#### Proximal Outcomes: Sibling Behavior & Adults with ASD (Timing indicated below)

1. **Sibling Plan of Action (T2)**. Siblings will submit a written plan of action at the final session; control participants will complete this plan at Time 2. We will use a template on which siblings will detail their short- and long-term goals with respect to family future planning and concrete next steps. Researchers will rate each plan according to the following criteria: (1) inclusion of short- and long-term goals and next steps, (2) appropriate scope of next steps, (3) alignment with the needs and/or preferences of the adult with ASD, (4) accuracy (e.g., are they identifying the right resources to meet the identified goal?), and (5) sufficient detail (e.g., including the names and phone numbers of actual resources vs. making vague plans). At the 3-month follow up time point, we will assess whether or not the sibling attempted or achieved their primary short-term goal, the steps they took to achieve their goal, and concrete outcomes of the sibling's engagement in family future planning (e.g., family made an appointment with a special needs lawyer).
2. **Adult with ASD: Quality of Life (T1 & T3). Proxy report**: Siblings will rate their brother/sister's quality of life using the Life Experiences Checklist. This has been used as a proxy-report measure by family members and support staff to rate the QOL of adult with ASD. Five sections cover the individual's home environment, leisure activities, relationships, freedom, and opportunities. **Self-report**: Adults with ASD will complete the WHOQOL-BREF, a shorter version of World Health Organization Quality of Life assessment, the WHOQOL-100, which includes 26 items rated on a 5-point scale addressing physical and psychological health, social relationships, and environment. This measure has been used with adults with ASD, including [name] collaborative study with [name]. We will modify administration as described by Hong and colleagues to ensure greater accessibility across the autism spectrum.

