*Aim 3: To assess the outcomes of participation in the Siblings FORWARD program.* We will examine whether the program shows promise of being successful with the intended population by conducting two-way repeated measures ANOVAs examining main effects of intervention condition (Siblings FORWARD vs. control) and repeated for assessment (pre- post- and 3-month follow up) on measures for program targets (sibling problem solving skills, family communication, future planning self-efficacy, barriers to future planning, and knowledge of services and family future plans) and proximal outcomes (sibling plan of action and adult with ASD quality of life, perceptions of unmet needs, and family relationships). Post-hoc tests will be used in multiple comparisons between groups and within each group. Effect sizes (Cohen's d) will be calculated using the mean difference of the changes recorded from pre- to post-program. We will also analyze percent change and reliable change. If data are missing, analyses will be performed using the 'last observation carried forward' method for intention-to-treat analysis. We will examine descriptive statistics (mean, SD, confidence intervals) at the participant level for patterns and direction of change on outcome measures. We will conduct intent-to-treat analyses if there is program attrition. Finally, we will examine benefit of the program to control participants who elect to participate in the Siblings FORWARD program using one-way ANOVAs (pre to post-program) on treatment targets and proximal outcomes.

We will conduct a preliminary investigation of potential moderators of program effectiveness, including characteristics of the sibling (BAP), family (income, race/ethnicity, English as the primary language, number of family members with ASD), and adult with ASD (severity of ASD symptoms, problem behaviors, functional independence). We will calculate correlations between these variables and change scores in primary outcome variables, and independent samples t-tests between these variables and program completion status.

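### Aim 3 applies a three-occasion ANOVA and a pre-to-post Cohen's d to two proximal outcomes that are not measured on that schedule: the plan of action (T2 only) and quality of life (T1 and T3 only)

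*Combined protocol and SAP*

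**What the plan says.** Data Analysis, Aim 3 gives one inferential model for the RCT outcomes: a two-way repeated measures ANOVA with intervention condition as one factor, "repeated for assessment (pre- post- and 3-month follow up". It is applied to six program targets and to the "proximal outcomes (sibling plan of action and adult with ASD quality of life, perceptions of unmet needs, and family relationships". Effect sizes are to be "calculated using the mean difference of the changes recorded from pre- to post-program". Percent change and reliable change are also planned. If data are missing, "analyses will be performed using the 'last observation carried forward' method".

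The Proximal Outcomes section of Measures sets timing item by item. Item 1 is headed "Sibling Plan of Action (T2". The program arm submits its plan at the final session, and "control participants will complete this plan at Time 2". On scoring, "Researchers will rate each plan according to the following criteria", and five criteria follow. At three months the rating is not repeated. Instead, "we will assess whether or not the sibling attempted or achieved their primary short-term goal". Item 2, quality of life by proxy and by self-report, is labelled T1 and T3.

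The RCT paragraph under Procedures places T2 immediately after the program (4 months after enrollment for controls) and T3 three months later.

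**The concern.** A three-occasion model needs values at T1, T2 and T3, and a pre-to-post d needs values at T1 and T2. The schedule supplies neither set for the plan of action or for quality of life. Aim 3 lists post and 3-month follow-up as separate occasions, so T3 cannot stand in for post.

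What is at stake is pre-specification. An analyst who follows Aim 3 as written cannot produce the stated d for either outcome and must choose a substitute, possibly after seeing the data. The timeline (Table 4) ends with a grant application for a larger trial, so effect sizes from this pilot may well be used again. It should be settled beforehand which contrast each one describes.

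**Working it through.** The documents state no power, alpha or target effect for this analysis, so there is no figure to reproduce. The check sets the schedule against the model.

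**Inputs.** 36 siblings, 18 per arm (Procedures, RCT). Occasions come from the Program Targets heading and Proximal Outcomes items 1 and 2. The model and d come from Data Analysis, Aim 3.

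**Degrees of freedom.** With N = 36, 2 arms, k occasions and complete data, the between-subject df are (1, N − 2) = (1, 34) and the within-subject df are (k − 1, (k − 1) × 34).

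| Outcome | T1 | T2 | T3 | k | Within df | Pre-to-post d |
|---|---|---|---|---|---|---|
| Six program targets | yes | yes | yes | 3 | (2, 68) | computable |
| Plan of action rating | no | yes | no | 1 | (0, 0) | not computable |
| Quality of life | yes | no | yes | 2 | (1, 34) | not computable |

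Self-reported quality of life will have fewer error df, because only adults who are able to will complete it.

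**Unmet needs and family relationships.** Items 3 and 4 carry no time label. Their fit cannot be confirmed or denied, and they are not counted as failing. The count is therefore 2 of 6 + 4 = 10 outcomes.

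**Plan of action.** With k = 1 there is no time effect, interaction or change score, hence no change-based d, percent change or reliable change. Two possible substitutes do not help. The T3 item records goal attempt or achievement, which is a different variable. The first draft made in Session 1 (Table 3) exists in the program arm only, and no rating of it is described. What remains is the arm comparison at T2, with 34 error df and d = (program mean at T2 − control mean at T2) / pooled SD.

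**Quality of life.** With k = 2, a condition-by-time analysis over T1 and T3 has df (1, 34). Effect size, percent change and reliable change can all be taken from T1 to T3.

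**Does LOCF repair the gap?** For the plan rating there is no earlier value to carry. For quality of life, setting T2 = T1 makes every pre-to-post change exactly 0 with SD 0, so d becomes 0/0.

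*Illustration only.* With T2 copied from T1, all within-person variation lies in the T3 − T1 difference. The three-level F is (SS/2)/(SSE/68) = 34 × SS/SSE, the same value as the two-level F. At an assumed 5% level it would be read against F(2, 68) = 3.13 instead of F(1, 34) = 4.13, and P(F(1, 34) > 3.13) = 0.086. This assumes LOCF at an unscheduled visit and no sphericity correction. A Greenhouse-Geisser correction would restore 5%.

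**The case against.** The strongest reply is that Aim 3 lists the study's occasions and each outcome is meant to be analysed at those it has, since the Proximal Outcomes heading says that timing is given item by item. On that reading a condition-by-T1/T3 model for quality of life is still a two-way repeated measures ANOVA. Aim 3 also names a main effect of condition, between-group post-hoc tests and descriptive statistics with confidence intervals. With one occasion, the condition effect reduces to the T2 arm comparison, which is clearly intended because controls complete a plan at that time. Much of this stands: valid comparisons are within reach for both outcomes. It does not rescue the effect size, which is tied to pre-to-post change without exception, and it leaves the reduced models to inference.

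Three stronger readings are tempting, and the documents do not support them:

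- **That the plan inflates the false-positive rate for quality of life to 8.6%.** Aim 3 invokes LOCF for missing data. An assessment that was never scheduled is not missing in that sense, and nothing in the text directs filling T2 from T1.
- **That the plan of action has no usable analysis at all.** The condition effect and the between-group comparisons provide one at T2.
- **That one of the RCT's headline questions cannot be answered.** The Overview under Approach asks whether a plan was created, which is not the five-criterion rating affected here.

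**Conclusion.** The mismatch is real and rests only on the plan's own time labels. The pre-to-post d cannot be computed for the plan of action or for quality of life. The plan rating supports no repeated-measures or change analysis, and quality of life supports a two-level analysis but not the three-level one. This is a stated analysis that the schedule cannot supply, not merely a detail left out.

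The consequence is modest. This is a 36-family pilot with no stated primary endpoint or power, asking whether the program shows promise. All six program targets fit the model, and the program description treats quality of life as a longer-term benefit. No data are lost. The correction should be made before analysis, but it does not threaten the trial. The schedule finding needs no assumption about alpha, correlations or missingness.

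**What to change.** Amend Data Analysis, Aim 3:

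1. Limit the three-occasion ANOVA and the pre-to-post Cohen's d to outcomes measured at T1, T2 and T3.
2. Plan of action: compare arms on the T2 rating (difference with 95% CI, d from the T2 arm means), and compare the proportions who attempted or achieved the primary short-term goal at T3.
3. Quality of life: use a two-level condition-by-time analysis (T1, T3), which stays closest to the present text, or T3 adjusted for T1. Do this separately for proxy and self-report. Take effect size, percent change and reliable change from T1 to T3.
4. State that LOCF does not fill an unscheduled T2 value.

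When time points are stated for unmet needs and family relationships, match their analysis to them in the same way. How the five plan criteria become one score is a separate question, but the T2 comparison should name the score it uses.

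The cost is a few sentences. All the data are already planned, and no visit, measure or participant is added. Adding a T2 quality-of-life assessment would also reconcile that outcome with the model, but it is not needed.

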## **APPROACH**

### **Overview**

The goal of the proposed research is to develop and evaluate the Siblings FORWARD program using behavioral telehealth technology. First, we aim to develop the 6-session Siblings FORWARD program in collaboration with community organizations. Siblings, adults with ASD, and community providers will give feedback on the proposed program through focus groups and/or individual interviews. Second, feasibility of the Siblings FORWARD program will be evaluated through an open trial (N=5 families). We will assess recruitment capability, appropriateness of outcome measures, program acceptability, and viability of the procedures. Finally, we will conduct a pilot randomized controlled trial (RCT) (N=36 families) to examine effects on the proposed targets and whether sibling involvement led to the creation of a plan of action for future planning.

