## Siblings FORWARD Program Description

The goal of the Siblings FORWARD program is to increase siblings' skills, knowledge, and self-efficacy to enable them to assume a greater role in future planning for their brother/sister with ASD. Program completion is expected to be associated with a higher likelihood of developing and implementing a future plan of action that includes short- and long-term planning goals. In turn, improved future planning is expected to be associated with longer-term improvements in unmet needs, quality of life, and family relationships for the adult with ASD (Figure 1). The Siblings FORWARD program will be delivered in six sessions over a 4-month period. Siblings will participate in all interactive online sessions guided by an Arc family support staff member; the adult with ASD will participate in one session, when possible. To increase future uptake and scalability, the program will be delivered by community providers with expertise in serving adults with ASD and their families. Sessions will equip sibling participants with concrete skills necessary to actively engage in future planning. Sessions follow a deliberate sequence starting with assessment of siblings' current involvement and skills and motivational interviewing techniques to bolster siblings' motivation for future planning; followed by instruction on skills related to communication and problem-solving, education about existing services and systems; application of problem-solving and communication skills to their plan of action; incorporation of the adult with ASD into the planning process; and final application of skills to the creation of a document outlining concrete next steps for the sibling's involvement in future planning. Content is outlined in Table 3 and Appendix 2.

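### Aim 3 names no primary outcome and no group-by-time test, and its within-arm post-hoc tests cannot show a program effect

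*Combined protocol and SAP*

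**What the plan says.** The Overview gives the RCT's purpose as "to examine effects on the proposed targets and whether sibling involvement led to the creation of a plan of action for future planning". Under Aim 3 the aim is put this way: "We will examine whether the program shows promise of being successful with the intended population". No criterion for promise follows.

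The ANOVAs cover two groups of outcomes:
- Program targets: "sibling problem solving skills, family communication, future planning self-efficacy, barriers to future planning, and knowledge of services and family future plans". This is six measures when the two kinds of knowledge are counted separately, as the Measures section does.
- Proximal outcomes: "sibling plan of action and adult with ASD quality of life, perceptions of unmet needs, and family relationships". This is four, or five if proxy and self-reported quality of life are separated.

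The effects named are the main effects of condition and of assessment. The group-by-time effect is not mentioned. Then comes: "Post-hoc tests will be used in multiple comparisons between groups and within each group". No significance level, post-hoc procedure or adjustment is given.

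The moderator analysis uses "correlations between these variables and change scores in primary outcome variables". That term is not defined. The Measures section sorts variables into baseline characteristics, targets and proximal outcomes, and ranks none of them.

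The Siblings FORWARD Program Description says better planning should lead to "longer-term improvements in unmet needs, quality of life, and family relationships" for the adult with ASD. The Measures section lists the same three outcomes as proximal, a class it describes as expected to change with participation.

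**The concern.** The moderator analysis cannot be run until someone decides which outcomes are primary, and nothing requires that decision before the results are known.

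The tests named also do not isolate the program. A main effect of assessment pools the arms and is significant if both improve. A main effect of condition averages over Time 1, before any program has been delivered. A within-arm test compares an arm with its own past. Shared improvement is plausible here, because the Control Condition paragraph gives controls the same tip sheets and resource packet as Session 3. That paragraph also says the project should show that the program's outcomes justify its extra time and resources over tip sheets, which is a between-arm question.

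At stake is the reading of promise and the larger grant application listed in Table 4. A report that the program arm improved significantly and the control arm did not could be offered as support when the program added nothing.

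**Working it through.** The plan states no alpha, power, effect size or error rate, so there is no figure of its own to reproduce.

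**Inputs from the documents:** 18 siblings per arm (Procedures, RCT); six targets measured at Times 1, 2 and 3 (Measures); plan of action rated at Time 2 only; quality of life at Times 1 and 3 only; no timing given for unmet needs or family relationships.

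**Assumptions:** two-sided 0.05 per test, normal data, complete follow-up, correlation 0.6 between any two time points, and, in step 1 only, an equal gain of 0.5 SD in both arms.

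**1. Equal true gain in both arms, within-arm tests only**
- SD of the change = √(2 × (1 − 0.6)) = 0.894 SD.
- Standardised change = 0.5 / 0.894 = 0.559.
- Noncentrality = 0.559 × √18 = 2.37, with 17 degrees of freedom and critical value 2.11. Power per arm = 0.609.
- Exactly one arm significant: 2 × 0.609 × 0.391 = 0.476. Simulation gave 47%.
- Only the program arm significant: 0.609 × 0.391 = 0.238, about 24%.
- Sensitivity of the one-arm-only figure to the correlation: 49% at 0.4, 50% at 0.5, 39% at 0.7, 20% at 0.8. The program-arm-only figure is half of each.

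**2. No true effect, results that could be cited in the program's favour** (simulation, 18 per arm)
- Favourable between-arm difference at Time 2 or Time 3, per target: 4.3 to 4.4%. As a check, two one-directional tests at 2.5% cannot exceed 5% together, and overlap brings this down.
- Across six independent targets: 1 − (1 − 0.043)^6 = 0.23, or 1 − (1 − 0.0438)^6 = 0.24.
- Also counting a favourable program-arm change from Time 1 to Time 2 or Time 3: 8.5% per target, and 1 − (1 − 0.0848)^6 = 0.41 across six.

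**3. Effect of correlated outcomes.** This used ten outcomes at their own measurement times (unmet needs and family relationships assumed at all three), within-person correlation 0.5, and 600 simulated trials per setting (error about 4 points). A favourable between-arm difference at Time 2 or 3 on any outcome falls from 36% to 19% as the between-outcome correlation goes from 0 to 0.7.

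**The case against.** Four points can be made for the plan.

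- **It is a pilot.** It has 36 families, already plans Cohen's d, confidence intervals and reliable change, calls its moderator work preliminary, and defers larger trials to later. This stands as far as it goes: strict familywise control over all outcomes is not required. It does not supply the missing primary outcome or turn a within-arm test into evidence of a program effect.
- **The documents do not say the tests are unadjusted; they are silent.** A post-hoc procedure may carry its own correction or follow only a significant ANOVA. This stands. Such a correction would not act across outcomes: in the ten-outcome simulation, Bonferroni within each outcome still left a 39% to 23% chance of some significant post-hoc result in either direction, as the between-outcome correlation rose from 0 to 0.7.
- **A two-way ANOVA would ordinarily produce the interaction,** and the planned Cohen's d uses differences in pre-to-post change. That is fair, but the interaction is not named as the test of interest.
- **Chance findings of promise can be exaggerated.** A reader might count nine post-hoc comparisons per target (three between arms, six within), get 31% per target and 89% across six independent targets, and infer that promise is likely by chance alone, or that almost any data set would yield something to cite. The documents do not support that. The nine include a between-arm test before the program starts, tests within the control arm, Time 2 against Time 3, and results in the wrong direction. Nor can nine tests apply to every outcome, given when the plan of action and quality of life are measured.

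**Conclusion.** The concern holds in a limited form. No primary outcome is designated, the outcomes used in the moderator analysis are undefined, the group-by-time effect is not named, and within-arm tests are planned with no stated adjustment.

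Under an equal 0.5 SD gain in both arms, about 47 to 48% of trials would show one arm significant and the other not, and about 24% only the program arm. With no true effect, about 23 to 24% would show a favourable between-arm difference at Time 2 or 3 on at least one target, or 41% if favourable program-arm changes also count. These figures rest on the assumed 0.05 per test, correlation 0.6, complete data and, for the last two, independent targets. None exceeds one half, so they do not show that promise is likely by chance alone.

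A reader might also infer that the adult outcomes are long-term only and wrongly tested. The documents disagree with each other on this: the Program Description points one way and the Measures section the other. The passages need reconciling.

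A short stretch between Preliminary Studies and Approach was not in the text reviewed. It is an unlikely place for a primary-outcome definition, but this could not be checked.

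**What to change.** Before outcome data are examined:

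1. Name one program target as primary, the sponsor's choice among the six. Give it a single test: the between-arm difference in change from Time 1 to Time 2 (the group-by-time contrast).
2. Use that target as the primary outcome variable in the moderator analysis.
3. For the other targets and the proximal outcomes, report between-arm estimates with confidence intervals, labelled exploratory. Use the difference in change where a Time 1 value exists and the difference at Time 2 for the plan of action.
4. Report within-arm changes as means with confidence intervals and no tests.
5. Reconcile the Program Description with the Measures section on whether adult quality of life, unmet needs and family relationships are expected to change within the study.

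The cost is analysis wording only, with no added participants, visits or measures. The downside is fewer nominally significant results to cite. One primary suits this size better than Bonferroni over ten outcomes. By the normal approximation, the effect detectable with 80% power at 18 per arm is (1.96 + 0.84) × √(2/18) = 0.93 SD of the analysed variable at 0.05, against (2.81 + 0.84) × √(2/18) = 1.22 at 0.005.

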Siblings and Adults with ASD. *Siblings* will be enrolled in three focus groups (N=18-24), the open trial (N=5), and the RCT (N=36). For focus groups, siblings who live in the greater Boston area will be enrolled. For the open trial and RCT, siblings will be enrolled regardless of their geographic location; this is possible due to the telehealth delivery format. Sibling inclusion criteria include (1) one or more adult brother(s) or sister(s) with ASD who are either biologically related and/or were raised in the same family of origin (e.g., adopted, step, or foster siblings), (2) age 18+, and (3) English fluency. Siblings will be excluded if they have a disability that would interfere with their ability to engage meaningfully in future planning for the adult with ASD. *Adults with ASD* (N=8-10) will participate in individual interviews during the first stage of the project and will complete self-report measures during the open trial and RCT if capable (with support if needed). Inclusion criteria for the adults with ASD include (1) an ASD diagnosis, (2) an adult brother/sister (i.e., a sibling), (3) age 21+, and (4)

Table 2: Community Advisory Board	
Name	Expertise / Role
[name]	Adult with ASD
[name]	Adult sibling; Co-founder of Sibling Leadership Network
[name]	Parent of youth with ASD & lawyer
[name]	Arc of Massachusetts
[name]	Director of Adult Services, AANE, & parent of youth with ASD

English fluency if verbal. For the focus groups, adults with ASD will be excluded if their abilities would preclude participation in an interview about future planning (e.g., due to significant cognitive or language challenges).

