**Table 3: Program Description**

Target	Description
Session 1: Assessment & Motivation (Sibling) – 75 minutes	The initial session will assess the extent to which future plans are in place, the extent to which the sibling is informed about future plans, siblings' perceptions of their own and their families' motivation and readiness to engage in the process, family values regarding family roles and care preferences, and initial goals for sibling involvement in family future planning for the adult with ASD. This session will include a motivational interviewing component to increase siblings' engagement with future planning. Finally, the sibling will draft a first version of their plan of action, including high-level goals. Between-session tasks: (1) learn about the family's existing future plans (if any) and (2) refine their goals for program participation and role in the life of their brother/sister with ASD.
Session 2: Family Communication (Sibling) – 60 minutes	Siblings will be taught to use effective communication skills with their family members (e.g., parents and the individual with ASD). The sibling will be given instruction in basic communication skills (e.g., using "I" statements, reading others' body language, maintaining a collaborative tone, etc). Then, he/she will practice these skills in session by role-playing how they might talk to family members about their initial plan of action that was outlined in Session 1. The sibling will set specific goals regarding communicating with family members (parents, brother/sister with ASD, other siblings, etc.) about specific topics identified in session (e.g., financial planning). Between-session assignment: work toward meeting the family communication goals outlined in session.

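### LOCF is the only missing-data method for the RCT outcomes, is never tested against another assumption, and cannot be applied to the plan of action or goal attainment

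*Combined protocol and SAP*

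**What the plan says.** Data Analysis, Aim 3, gives one rule for missing data: "If data are missing, analyses will be performed using the 'last observation carried forward' method for intention-to-treat analysis". In the text available for review there is no mixed model, multiple imputation, observed-case comparison or other sensitivity analysis. The results that pass through this rule include the repeated-measures ANOVAs and two summaries of change: "Effect sizes (Cohen's d) will be calculated using the mean difference of the changes recorded from pre- to post-program" and "We will also analyze percent change and reliable change".

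The outcomes covered by the rule are not all measured at the same times:

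- Program targets are measured at Time 1, Time 2 and Time 3 (T1, T2, T3).
- The plan of action is rated once: "Siblings will submit a written plan of action at the final session; control participants will complete this plan at Time 2".
- Goal attainment is assessed once: "At the 3-month follow up time point, we will assess whether or not the sibling attempted or achieved their primary short-term goal".
- The quality-of-life item is headed "Adult with ASD: Quality of Life (T1 & T3", so it has no T2 value.
- Adults with ASD "will complete self-report measures during the open trial and RCT if capable (with support if needed", so some will have no self-report at any wave.

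An earlier form of the plan of action does exist. In Session 1 of Table 3, "the sibling will draft a first version of their plan of action, including high-level goals". That draft belongs to the program arm only and is not listed as a rated measure.

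Under Aim 2, siblings who complete the program are compared with those who do not on demographic and clinical characteristics.

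**The concern.** LOCF fills a value missing at T2 with the T1 value. The sibling then has zero change, zero percent change and no reliable change. The arm comparison is unbiased only if lost siblings would not have changed, or if the errors in the two arms happen to cancel. Nothing in the plan examines either condition. The Aim 2 completer comparison shows who left but does not re-estimate the effect.

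For the plan of action and goal attainment the rule cannot be followed, because no earlier rated value exists. The Overview names creation of a plan of action as one of the things the RCT is meant to examine.

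What is at stake is the pilot's effect estimate. Aim 3 uses between-arm comparisons, Cohen's d and reliable change to judge whether the program is promising, and Table 4 schedules a grant application for a larger trial. There is no confirmatory test, so the harm is a misleading estimate carried forward, not a false efficacy claim.

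**Working it through.** **Inputs.** From the documents: 36 siblings, 18 per arm (Procedures, RCT), and the measurement times above. The documents give no attrition rate, effect size, SD or power basis, so the plan has no figure of its own to reproduce. Assumed: SD 1 at each wave, correlation 0.6 between waves, and loss after T1 unrelated to outcome. Loss is written program/control.

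**T2 mean difference.** With mean gains gP and gC and loss fractions mP and mC:

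LOCF difference = (1 - mP) × gP - (1 - mC) × gC

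| Case | Calculation | LOCF | True |
|---|---|---|---|
| gP 0.5, gC 0, 10%/10% | 0.90 × 0.5 | 0.45 | 0.50 |
| same, 20%/20% | 0.80 × 0.5 | 0.40 | 0.50 |
| same, 30%/30% | 0.70 × 0.5 | 0.35 | 0.50 |
| gP 0.8, gC 0.3, 20%/20% | 0.80 × 0.8 - 0.80 × 0.3 | 0.40 | 0.50 |
| gP 0.8, gC 0, 25%/5% | 0.75 × 0.8 | 0.60 | 0.80 |
| both 0.6, 15%/5% | 0.85 × 0.6 - 0.95 × 0.6 | -0.06 | 0 |
| both 0.6, 30%/5% | 0.70 × 0.6 - 0.95 × 0.6 | -0.15 | 0 |

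Equal loss m shrinks the difference to (1 - m) of its true value, whether or not controls change. Unequal loss creates a difference where none exists if both arms improve.

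**Cohen's d.** The plan does not name the standardising SD; the LOCF change SD is used here. Without loss the change variance is 2 × (1 - 0.6) = 0.8. With equal loss m, a program gain of 0.5 and unchanged controls, vC = (1 - m) × 0.8 and vP = vC + m × (1 - m) × 0.25. At m = 0.2, vC = 0.64 and vP = 0.68, so d = 0.40 / sqrt(0.66) = 0.492, against 0.5 / sqrt(0.8) = 0.559 without loss. At 10% and 30% it is 0.526 and 0.457. So d falls by about 6%, 12% and 18%, less than the mean difference, because LOCF also shrinks the SD. Simulation with 18 per arm (40,000 trials per T2 scenario) gave 0.57 without loss, then 0.54, 0.50 and 0.47.

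**Inference under unequal loss (same simulation).** For a true 0.8 SD at 25%/5%, d falls from 0.92 to 0.71 and coverage of the 95% interval is 89%. With no true difference at 30%/5%, d is -0.19 and type I error is 9%.

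**T3.** Let total loss m be equal in the arms, s the share of loss falling after T2, and D2 and D3 the true effects:

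LOCF at T3 = (1 - m) × D3 + s × m × D2, so bias = m × (s × D2 - D3)

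LOCF overstates a fading effect only if s exceeds D3/D2. At m = 0.2:

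- 0.8 fading to 0.4: 0.32 + 0.16 × s = 0.32, 0.40, 0.48 for s = 0, 0.5, 1.
- 0.5 fading to 0.4: 0.32 + 0.10 × s = 0.32, 0.37, 0.42.

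Quality of life has only T1 to carry, so a true 0.40 at T3 with 20% loss becomes 0.80 × 0.40 = 0.32.

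**When LOCF is right.** Suppose lost program siblings gain nothing and controls are unchanged, 20%/20%. The truth is 0.80 × 0.5 = 0.40. LOCF gives 0.40; an observed-data analysis gives 0.50.

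**Check with loss related to T1.** In 5,000 trials with correlation 0.5 and dropout likelier at low T1 scores, a true 0.80 became 0.63 under LOCF with similar dropout in both arms and 0.51 with heavier program-arm dropout. Baseline-adjusted analysis of observed data gave 0.80 both times.

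**The case against.** The strongest objection is that the case for replacing LOCF is mixed. With equal loss, baseline-adjusted analysis of observed data has slightly larger total error: RMSE 0.31 against 0.29 at 20%/20%, and 0.33 against 0.30 at 30%/30%. If lost program siblings gain nothing, LOCF is right and the replacement overstates. This stands, and it is why the replacement should not be used alone. It does not rescue LOCF alone, which is also a single unexamined assumption.

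Second, the worst cases are assumed. With 18 per arm, 30%/5% means about five siblings against one, and nothing in the documents predicts that. With equal 20% loss, d moves from 0.57 to 0.50, about a fifth of its standard error (sqrt(2/18 + 0.5²/72) = 0.34), and towards no effect. This is fair and limits the severity. But the direction is not guaranteed: unequal loss can favour either arm, and T3 can be overstated.

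Third, the plan does report retention, a completer comparison and change-score descriptives with confidence intervals. A reader would see how much was lost, but none of these re-estimates the arm difference under another assumption.

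Fourth, stopping sessions is not the same as losing data, since the university team collects sibling questionnaires by mail. This is true, but program-arm T2 is tied to finishing the program, so it has no defined date for a sibling who stops.

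Fifth, placing a T2-only measure in a three-wave ANOVA is a separate mismatch, and inability to self-report is a design feature. Both stand. The simulations also tested baseline-adjusted regression at T2, not the full repeated-measures model, and examined control-based imputation for its mean only.

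**Conclusion.** The concern holds. Two parts need no assumption: LOCF is the sole missing-data method with nothing set against it, and it cannot be applied to a missing plan of action or to goal attainment.

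The size of the bias is conditional, because no attrition rate is given. With loss unrelated to outcome, equal loss of 10% to 30% dilutes the T2 mean difference by the same percentage. Unequal loss can produce a spurious difference, from -0.06 SD at 15%/5% to -0.15 SD at 30%/5% when both arms gain 0.6 SD. T3 can be biased either way. If lost siblings would not have changed, there is no bias at T2. The trial's data cannot separate these situations, so the plan should show the result under more than one. For a 36-family pilot this is a change that should be made, not a fatal flaw.

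**What to change.** In Data Analysis, Aim 3, replace the LOCF sentence with analysis of all observed data from all randomised siblings:

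1. Scale outcomes measured at T1, T2 and T3: a likelihood-based repeated-measures model adjusted for the T1 value, with small-sample degrees of freedom.
2. Quality of life: a baseline-adjusted comparison at T3.
3. Plan of action and T3 goal attainment: a direct between-arm comparison, with the number missing in each arm.

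Report adults with ASD who cannot self-report as a separate count and do not impute them. State which rule covers unmet needs and family relationships, whose timing is not given, and how the three-category family communication item will be modelled.

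Add one sensitivity analysis in which lost program-arm siblings do not keep the program gain, such as control-based imputation. On the assumptions above it gives 0.40 at 20%/20%, which is the truth if those siblings gain nothing, and 0.00 instead of -0.15 in the 30%/5% no-difference case.

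In Procedures, RCT, state that siblings who stop sessions are still asked for T2 measures (including the plan template) and T3 measures at the control-arm times, 4 and 7 months after enrollment. This should be settled before enrollment, since T2 data never requested cannot be recovered.

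The cost is analysis wording, standard software and continued questionnaires. The main model relies on data being missing at random and overstates if lost siblings gain nothing (0.50 against 0.40 at 20%/20%), so the sensitivity analysis is essential. Intervals are wider under equal loss: SE 0.30 against 0.27 at 20%/20%. For a true 0.8 SD at 25%/5% the total-error ranking reverses: RMSE 0.30 against 0.35 for LOCF.
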